Visits 5 – 8 (Weeks 4, 8, 12 and 18)

Subjects will attend the site for safety, PK and efficacy assessments.

Imaging Sub-Study

Subjects participating in the imaging sub-study will also undergo an MRI procedure on or immediately following Visit 7 (Week 12). All safety, PK and efficacy assessments will be performed prior to performing the MRI.

Visit 9 – Week 24 (End-of-Study or Early Exit Visit)

Subjects will attend the site for final safety, PK and efficacy assessments and will return any unused rescue medication, and their ePRO device.

Imaging Sub-Study

Subjects participating in the imaging sub-study will undergo an MRI procedure on or immediately following Visit 9 or the early exit visit. All safety, PK and efficacy assessments will be performed prior to undergoing MRI.

If a subject participating in the imaging sub-study exits the main study early, an early exit visit will be performed, and an early exit MRI acquired on or immediately following the visit. If the MRI is within 2 months of the previous MRI scan, then an MRI does not need to be performed, except in the case that the previous MRI was performed prior to dosing and the early exit MRI will be the only MRI collected post treatment administration. The early exit MRI will be conducted in this instance.

	
Visit 10 – Week 52 (for Imaging Sub-Study Only)
 
Only subjects participating in the optional imaging sub-study will perform Visit 10.
 
After Visit 9, no efficacy assessments, PK, or safety assessments apart from AE recording will be performed. Subjects will not be required to refrain from any medications/procedures after Visit 9. The subject will be treated as per standard of care by their physician during this time.
 
At Visit 10 AEs and concomitant medications/procedures will be collected for the timeframe between Visit 9 and 10 to capture any changes in the subject's health status. Eligibility to conduct imaging will be reviewed based on MRI-sub-study exclusion criteria. If the subject remains eligible to undergo the final MRI based on these criteria and has a negative result on a urine pregnancy test (for females of childbearing potential) they may proceed to have the final MRI scan.

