Study Day	-56 to -15	1	85	169	365
MRI Specific Visit Window		Baseline MRI on a separate day. Within 5 days before IMP administration.	+14 days	+14 days	±14 days
Informed consent for Imaging Sub-Study ¹	X				
Medical history incl. OA history					X
Comeds & procedures (& any changes)					X
MRI ²	X	X	X	X	X
Review exclusion criteria for Imaging sub-study	X ³	X ³	X ³	X ³	X ³
Record and assess AEs					X
Urine sample for pregnancy test ⁴	X	X	X	X	X

¹ Must be obtained before performing any imaging related procedures.
² MRI following the IV injection of macrocyclic gadolinium-based contrast agent, as described in the MRI Imaging Charter. At visits after IMP injection, MRI must be completed after visit efficacy, safety, and PK procedures are performed. MRI may occur on the same day as these other assessments if the MRI scan is acquired as the final procedure.

³ Must be completed prior to imaging
⁴ A urine pregnancy test will be performed on all women of childbearing potential prior to imaging. For Visit 2, the pregnancy test does not need to be repeated prior to IMP administration.

Notes: AEs=Adverse events; IMP=Investigational medicinal product; IV=Intravenous; MRI=Magnetic resonance imaging; OA=Osteoarthritis.

TABLE OF CONTENTS

	Page
SIGNATURE PAGE.....	2
INVESTIGATOR AGREEMENT AND SIGNATURE PAGE.....	3
SYNOPSIS.....	4
SCHEDULE OF EVENTS	15
IMAGING SUB-STUDY ADDITIONAL SCHEDULE OF EVENTS	18
TABLE OF CONTENTS	19
LIST OF TABLES	23
LIST OF FIGURES	24
LIST OF ABBREVIATIONS	25
1. INTRODUCTION AND BACKGROUND.....	27
1.1 Background of the Disease and Treatment Options	28
1.2 Summary of Non-clinical and Clinical Data.....	29
1.2.1 Non-clinical Summary	29
1.2.2 Clinical Summary	31
2. RATIONALE	33
2.1 Dose Selection	33
2.1.1 Dose Justification Based on Local Exposure.....	33
2.1.2 Dose Justification Based on Systemic Exposure	34
2.2 Risks/Precautions	35
3. STUDY OBJECTIVES.....	38
3.1 Primary Objective	38
3.2 Secondary Objectives.....	38
4. INVESTIGATIONAL PLAN	39
4.1 Overall Study Design.....	39
4.2 Duration of Subject Participation.....	42
4.3 Safety Oversight.....	43
4.4 Pre-Defined Study Stopping Rules	44
5. SELECTION AND WITHDRAWAL OF SUBJECTS	46
5.1 Number of Subjects.....	46
5.2 Inclusion Criteria	46
5.3 Exclusion Criteria	47
5.4 Withdrawal of Subjects.....	50
6. RANDOMIZATION, BLINDING AND UNBLINDING	52
6.1 Randomization	52
6.2 Blinding.....	52
6.3 Unblinding	52
7. STUDY TREATMENTS	54
7.1 IMP Dosage Forms/Formulation	54

7.1.1	EP-104IAR.....	54

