In the GLP dog toxicology study, the primary local effects were synovial granulomatous inflammation and synovial degeneration and/or necrosis. The granulomatous inflammation appears to be due to the presence of particles in the synovium, while the degeneration appears to be due to high local levels of steroid. These effects were dose related. At clinically relevant doses, these effects were minimal to mild and considered not clinically significant. In the Phase 1 clinical study, there were no obvious local toxicity findings; however close attention should be paid to administration site adverse events (AEs), and examination of the knee. As a precaution, detailed knee examinations will be performed at all scheduled visits, with particular attention paid to any findings that could be indicative of a severe inflammatory response without another known cause, see Section [9.1.5.3](#).

It is expected that the frequency and severity of any AEs will be similar to those reported for other marketed IA corticosteroid injections.

Overall, it is believed that the known and unknown risks associated with EP-104IAR can be adequately monitored throughout the clinical study and are outweighed by its potential benefit in OA.

Imaging Sub-Study Risks

Side effects associated with the use of Gadolinium Based Contrast Agents (GBCA) are usually mild to moderate in intensity and transient in nature. The most frequently observed physiologic reactions are headache, nausea, paraesthesia, vomiting, dizziness, a sensation of heat, cold and/or pain at the injection site, and mild hypersensitivity reactions such as erythematous rash and pruritus ([Fraum, et al., 2017](#)).

More serious adverse reactions to GBCA are hypersensitivity (immediate and delayed up to 7 days), anaphylactic, and anaphylactoid reactions that may be very rarely severe, life-threatening or have a fatal outcome, particularly in patients with a history of allergy. Hypersensitivity reactions are also more common in patients with prior adverse reactions to GBCA ([Fraum, et al., 2017](#)). Patients with a history of allergy, or with a prior adverse reaction to a GBCA will be excluded from this sub-study.

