Between visits, subjects will continue to record their daily, weekly and monthly (every 4 weeks) assessments at home using the ePRO device provided.

Imaging Sub-study:

Subjects participating in the imaging sub-study will also undergo an MRI procedure at or immediately following Visit 7 and at or immediately following Visit 9 (or the early exit visit).

All safety, PK and efficacy assessments will be performed prior to receiving the MRI. The MRI may be performed on a separate day to these assessments.

To ensure the subject is safe to proceed with imaging procedures, a urine pregnancy test will be performed and eGFR will be calculated based on the most recent creatinine value.

Visit 10 – Week 52 (Imaging Sub-Study Only)

Only subjects participating in the optional imaging sub-study will perform Visit 10.

After Visit 9, no efficacy, PK, or safety assessments (apart from AE recording) will be performed. Subjects will not be required to refrain from any medications/procedures after Visit 9. The subject will be treated as per standard of care by their physician during this time.

At Visit 10 AEs and concomitant medications/procedures will be collected for the timeframe between Visit 9 and 10 to capture any changes in the subject's health status.

Eligibility to conduct imaging will be reviewed based on imaging-sub-study exclusion criteria, where the eGFR calculation will be based on the Visit 9 creatinine value, unless more recent results are available. If the subject remains eligible to undergo the MRI based on these criteria and provided a negative result on a urine pregnancy test (for females of childbearing potential) they may proceed to have the final MRI scan. The detailed schedule of assessments is provided in Section [9.2](#) and the [Schedule of Events](#).

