9.1.3.2 Magnetic Resonance Imaging

Imaging Sub-Study Only

The imaging sites will be qualified to ensure research conversance and suitability of facilities. The imaging site personnel will be trained by imaging experts prior to initiation of the study. Imaging data will be redacted to ensure that subject identifiers are removed, and the image will be transmitted to a core imaging laboratory, stored in a central imaging database for the study and assessed by central expert reader(s).

All images (MRI) will be read centrally by a blinded radiologist appointed by the central imaging lab, who is not directly involved in the treatment or clinical evaluation of the subject. The blinded radiologist will remain blinded for the Week 52 MRI scans.

DCE-MRI of the index knee will be used to perform analyses that will potentially inform on the duration and local safety of EP-104IAR. These analyses will include measurements related to synovial inflammation (synovial thickness, synovial blood flow), cartilage volume and the status of the articular cartilage (cartilage morphology) assessments. A macrocyclic GBCA will be administered intravenously to subjects, prior to the MRI at baseline, and Weeks 12, 24, and 52, in accordance with the instructions provided in the MRI Imaging Charter which will also detail the exact imaging protocol and MRI sequences.

If feasible, the reader of the images should remain the same for the duration of the study, to minimise the risk of inter-reader variability.

DCE-MRIs will be performed using a validated protocol at the time points specified in the [Schedule of Events](#). The minimum requirement will be for the MRI provider to use a 1.5 or 3 Tesla scanner. The MRI protocol and scanner settings will be calibrated between the imaging sites and maintained for all sites for the duration of the study.

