9.2.5.8 Visit 10 (Week 52 Day 356 ±14 days)

Imaging Sub-Study Only

- Review MRI eligibility criteria
- Urine collection for pregnancy test (if applicable)
- MRI
- Recording of AEs and changes in conmed use since Visit 9.
- Recording of medical and OA history since Visit 9

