10.3.2 Serious Adverse Events

An SAE must be immediately reported to the Sponsor within 24 hours of awareness.

The Investigator must complete the SAE form and verify the accuracy of the information recorded with the corresponding AE, concomitant medication, and medical history eCRF page(s).

Where possible, the Investigator should report a diagnosis rather than signs and symptoms. In case of a fatal outcome, the Investigator should provide a working diagnosis (event which caused outcome, e.g., fatal myocardial infarction) instead of reporting only death; and an autopsy report with death certificate should be provided where possible.

The Investigator will report all SAEs (related or not related) from the time the informed consent is signed until 24 weeks after IMP administration. SAEs starting before dose administration must be identified as such.

If a subject dies during their study participation, or if the Investigator becomes aware of the death of a discontinued subject within 24 weeks after dose administration, the death must be reported to the Sponsor, whether considered treatment-related or not.

Imaging Sub-Study

For subjects participating in the imaging sub-study, the Investigator will continue to report any SAEs (related or unrelated) or deaths (related or unrelated) until the subject completes their final imaging visit (i.e., Visit 10), or withdraws from the sub-study.

The onset date of the AE is defined as the onset of signs and symptoms or a change from baseline. The onset date of the SAE is defined as the date the signs and symptoms/diagnosis became serious, i.e., met at least 1 of the criteria for seriousness listed in Section 10.1.4. The resolution date of the SAE is defined as when the symptoms resolve, or the event is considered chronic (e.g., sequelae) or stable, and/or if the seriousness criteria are no longer applicable. Serious adverse events that are ongoing at the time of death are considered unresolved.

All recorded SAEs, regardless of relationship to investigational product, will be followed up until resolution, stabilization, or the subject is lost to follow-up and cannot be contacted. In circumstances where the Investigator is unable to contact the subject (or his/her relatives), the Investigator must provide a written statement (recorded in the subject's source documents), confirming that the subject is lost to follow-up. At a minimum, the following should be provided at the time of the initial SAE report:

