- Subject number, age, and gender/sex.
- Event description (including onset date of the event and reason for it being considered serious).
- Relationship to investigational product (i.e., causality).

- Name of the investigational product (including drug dose and administration dates).
- Investigator name and address.
- Name of the reporter (including site name or number and country).
- Dated signature of the Investigator or sub-Investigator.

Additional follow-up information, if required or available, must be provided immediately (within 24 hours of awareness) following Investigator (or site) awareness of the information.

Preliminary reports will be followed by detailed descriptions which will include information from hospital case reports, autopsy reports/certificates (in case of death) and other documents when requested and applicable.

The Sponsor, or its delegate, is responsible for expedited reporting to the relevant Regulatory Authorities, to Investigators and to local and central IRB/IEC as per local regulations.

Any SAE considered to have a causal relationship (i.e., related) to the investigational product and discovered by the Investigator at any time after the study is completed should be reported to the Sponsor. A rationale for the assessment of a causal relationship must be provided by the Investigator together with the SAE form. Any safety information that is obtained after database lock of the clinical database will be documented only in the safety database and, if applicable, will undergo expedited reporting.

Additional detail regarding SAE reporting will be provided in the study documentation.

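### Delayed reactions to the final gadolinium dose have no planned capture: the protocol gives a window of up to 7 days, but scheduled contact and sub-study SAE reporting end with the Week 52 imaging visit

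*Protocol*

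**What the plan says.** The imaging-risk text in Section 2.2 names "hypersensitivity (immediate and delayed up to 7 days), anaphylactic, and anaphylactoid reactions" as the more serious reactions to the contrast agent, and says that they may very rarely be severe, life-threatening or fatal. Section 9.1.3.2 gives intravenous contrast "prior to the MRI at baseline, and Weeks 12, 24, and 52".

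On adverse events at the last scan, Section 4.1 says: "At Visit 10 AEs and concomitant medications/procedures will be collected for the timeframe between Visit 9 and 10". It then describes an eligibility check and a pregnancy test, after which subjects who pass are told "they may proceed to have the final MRI scan"; the synopsis reads the same way. Footnote 2 of the imaging schedule of events says of visits after injection that "MRI must be completed after visit efficacy, safety, and PK procedures are performed". The Visit 10 procedure list in Section 9.2.5.8 puts the MRI earlier and then lists "Recording of AEs and changes in conmed use since Visit 9". Section 10.3.1 ends the AE reporting period at Visit 9 and has no sub-study extension.

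On serious events, Section 10.3.2 has the investigator report SAEs and deaths in sub-study subjects "until the subject completes their final imaging visit (i.e., Visit 10), or withdraws from the sub-study". Its open-ended clause after the study reads "Any SAE considered to have a causal relationship (i.e., related) to the investigational product" and does not mention the contrast agent.

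Under Section 5.4, a subject who leaves the main study early also leaves the sub-study, and normally has an exit scan on or just after the exit visit. A subject who reacts to contrast is withdrawn from the sub-study.

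**The concern.** The contrast dose is given only for research, and the protocol itself states how long a hypersensitivity reaction may take to appear. The reporting period should last at least that long after the last dose. At Week 52 it does not: the subject leaves Visit 10 with no later contact planned, and the sub-study's SAE obligation ends at that point.

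At stake are participant protection and the completeness of contrast-safety reporting. A delayed reaction after the final scan, serious or not, would reach the sponsor only if someone volunteered it. The SAP plans a table of MRI-related treatment-emergent events (Sections 1.2 and 3.8.4.1), so reporting such reactions is intended, but the SAP adds no data collection after Visit 10.

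**Working it through.** **1. Planned follow-up after the last scan.** Protocol Section 4.2 gives up to 6 weeks of screening, about 2 of washout and baseline, 24 of follow-up, and 28 more for one imaging visit.

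- Main study: 6 + 2 + 24 = 32 weeks, as stated.
- Sub-study: 32 + 28 = 60 weeks, as stated.
- Last visit: 24 + 28 = Week 52, which is Day 1 + 52 × 7 = 365, as in the imaging schedule.
- Time left after Visit 10: 60 − (6 + 2 + 24 + 28) = 0 weeks.

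Planned surveillance is 0 days against a window of up to 7.

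**2. Do the earlier scans have the same gap?** For each scan, take its latest day and the earliest day of an AE contact that falls beyond 7 days. Windows are from the two schedules of events.

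| Scan | Latest day | Later AE contact, earliest day | Gap |
|---|---|---|---|
| Baseline | Day 1, before dosing | Visit 4: 15 − 3 = 12 | 11 days |
| Week 12 | 85 + 14 = 99 | Visit 8: 127 − 3 = 124 | 25 days |
| Week 24 | 169 + 7 + 14 = 190 | Visit 10: 365 − 14 = 351 | 161 days |
| Week 52 | Visit 10 | none | none |

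If the Week 12 scan window runs from a visit held on Day 88, the latest scan is Day 88 + 14 = 102 and the gap is 22 days. Section 9.2.5.8 puts Visit 10 at Day 356, not 365; on that figure the Week 24 gap is 356 − 14 − 190 = 152 days. Neither changes the result. For subjects who stay in the study, only the final scan lacks a later contact.

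**3. Order of events at Visit 10.** The synopsis and Section 4.1 describe AE collection for the interval since Visit 9, then eligibility, then the scan. Footnote 2 of the imaging schedule also points to the scan coming last. Section 9.2.5.8 lists AE recording after the MRI. The imaging schedule marks both at Visit 10 without an order. The order is therefore inconsistent.

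**4. What is captured after the Week 52 contrast dose.**

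- Immediate and serious: reportable, because the scan is part of Visit 10 and SAE reporting runs until that visit is completed.
- Immediate and non-serious: captured only if AEs are recorded after the scan. Section 10.3.1 closes the AE period at Visit 9, so the authority to record it also needs reconciling.
- Delayed and serious: outside sub-study SAE reporting. The post-study clause applies only if the event is attributed to the investigational product.
- Delayed and non-serious: no planned capture.

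**5. Early exit and withdrawal.** At early exit the AE period ends with the exit visit, while the scan is on or just after it. Main-study SAE reporting continues to 24 weeks after dosing, so serious events are partly covered. After Week 24 the sub-study extension is what carries SAE reporting, and withdrawal ends it. A subject withdrawn for a contrast reaction can therefore leave SAE reporting while still inside the 7-day window.

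**The case against.** The strongest reply is that much is already covered. Section 9.2.5.8 is the dedicated Visit 10 list, and a recording of AEs since Visit 9 made after the MRI would include the scan. Section 2 explains the scan-last rule as protecting main-study measures, so the footnote need not mean that AE recording closes before the Week 52 scan. An immediate SAE is reportable, and recorded SAEs are followed to resolution or stabilisation. Section 5.4 also has an AE that leads to discontinuation followed up. Known prior contrast reactors and people with a history of severe allergy are excluded, and severe reactions are called very rare. The MRI Imaging Charter, the sub-study consent form or other SAE documentation might contain post-scan instructions.

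Most of this stands, and it limits the point. A reader might infer that no reaction of any kind to the last contrast dose is captured. The documents do not support that: immediate SAEs are reportable, and one version of the procedure order captures immediate non-serious events. A reader might also treat one of the four contrast doses as wholly unobserved and conclude that the reaction rate is understated in proportion. That fails for the same reason. It also assumes constant risk per scan, although reactors are withdrawn along the way, and no per-scan rate is planned.

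The reply does not reach delayed reactions. No order of procedures on the day of the scan can record an event that starts several days later. Instructions in unseen manuals would not override the explicit end of reporting in Section 10.3.2.

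**Conclusion.** The point holds for delayed reactions to the last contrast dose: 0 days of planned surveillance against the protocol's own window of up to 7 days. Capture of immediate non-serious reactions at Visit 10 is uncertain because the sections disagree on order and on when AE reporting ends. Early-exit scans have a similar but smaller gap.

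This assumes that the scan is part of Visit 10 and that no document outside the protocol and SAP adds a later contact. The number of missed events cannot be estimated: neither document gives the sub-study size or a contrast-reaction rate.

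A reader might also infer that the 52-week safety objective is biased. Section 3.2 frames that objective around a single injection of EP-104IAR, so a missed contrast reaction at Week 52 does not bias it. The consequence is for participant safety and contrast-safety reporting in an optional exploratory sub-study. That is modest in scale, but the gap is cheap to close.

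**What to change.** - In Protocol Sections 10.3.1, 10.3.2 and 9.2.5.8, run AE and SAE reporting for sub-study subjects to 7 days after their last contrast scan. Include early-exit scans and subjects withdrawn after a contrast reaction.
- Add one telephone contact at about day 7 after that scan to the imaging schedule of events.
- State that AEs at Visit 10 are also recorded after the scan.
- Reconcile the synopsis, Section 4.1, footnote 2 of the imaging schedule, and Sections 9.2.5.8, 10.3.1 and 10.3.2 on the order of Visit 10 procedures and the end of AE reporting. Settle Day 356 against Day 365 at the same time.
- Include these events in the sub-study's own MRI-related AE summary. The main analysis in the SAP takes place before the sub-study finishes.

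The cost is amendment wording, one short call per sub-study subject, and about one more week of participation (60 + 1 = 61 weeks at most). No extra site visit or procedure is needed.
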